#### 8.1.2 Serious Adverse Event

A serious adverse event (SAE) is any experience that suggests a significant hazard, contraindication, side effect or precaution. It is any AE that results in any of the following outcomes:

**Protocol 18PEHH:**

A proof-of-concept study to evaluate the efficacy of Salmon Protein Hydrolysate Powder on energy increase and anti-inflammatory modulation in healthy males and females.

1. Death
2. A life-threatening adverse event
3. Inpatient hospitalization or prolongation of existing hospitalization
4. A persistent or significant disability or incapacity
5. A congenital anomaly/birth defect in the offspring of a participant who received the study treatment

Important medical events that may not be immediately life-threatening or result in death or hospitalization but may jeopardize the participant or may require intervention to prevent one of the outcomes listed above. Examples of such events are intensive treatment in an emergency room or at home for allergic bronchospasm; blood dyscrasias or convulsions that do not result in hospitalization; or the development of drug dependency or drug abuse.

### **8.1.3 Unexpected Adverse Reaction**

An unexpected adverse reaction is an adverse reaction, the nature and severity of which is not consistent with the applicable product information (e.g., Investigator's Brochure for an unapproved investigational product or package insert/summary of product characteristics for an approved product).

### **8.1.4 Laboratory Test Abnormalities**

The investigator must assess the clinical significance of all abnormal laboratory values as defined by the compendium of normal values for the reference laboratory.

Any treatment emergent abnormal laboratory result which is clinically significant, i.e., meeting one or more of the following conditions, should be recorded as a single diagnosis on the AEs form in the study record:

1. Accompanied by clinical symptoms
2. Leading to interruption or discontinuation of the investigational product
3. Requiring a change in concomitant therapy

This applies to any protocol and non-protocol specified laboratory result from tests performed after the first dose of the investigational product, which falls outside the laboratory reference range and meets the clinical significance criteria for liver and kidney tests as well as for hematology and clinical chemistry.

This does not apply to any abnormal laboratory result which falls outside the laboratory reference range but which does not meet the clinical significance criteria or those which are a result of an AE which has already been reported.

Any laboratory result abnormality fulfilling the criteria for a serious adverse event (SAE) should be reported as such, in addition to being reported as an AE in the study record.

## **8.2 Treatment and Follow-up of AEs and Laboratory Abnormalities**

### **8.2.1 Treatment and Follow-up of AEs**

AEs, especially those for which the relationship to the investigational product is suspected, should be followed up until they have returned to baseline status or stabilized.

If after follow-up, return to baseline status or stabilization cannot be established, an explanation should be recorded in the study record.

Protocol 18PEHH: A proof-of-concept study to evaluate the efficacy of Salmon Protein Hydrolysate Powder on energy increase and anti-inflammatory modulation in healthy males and females.

### **8.2.2 Treatment and Follow-up of Laboratory Abnormalities**

In the event of participant-initiated withdrawal or clinically significant unexplained abnormal laboratory test values, the participant will be withdrawn from the treatment and will remain in the study and be required to attend all remaining study visits as part of a safety arm.

### **8.3 Reporting of SAEs and Unexpected Adverse Reactions**

The qualified investigator will be responsible for classification of an AE as an SAE within 24 hours of notification. Causality should be signed off by the qualified investigator prior to reporting to ethics and regulatory bodies. Notification of any serious adverse events must be made in writing to the study sponsor. The IRB will be notified of all product related SAEs and unexpected adverse reactions.

KGK Science must notify the TPD of all serious adverse events and reactions as follows:

If it is neither fatal or life threatening, within 15 calendar days after the day on which the sponsor becomes aware of the information; and

If it is fatal or life threatening, must be reported as soon as possible, but not later than seven (7) days after the day on which the sponsor becomes aware of the information.

Protocol 18PEHH:	A proof-of-concept study to evaluate the efficacy of Salmon Protein Hydrolysate Powder on energy increase and anti-inflammatory modulation in healthy males and females.
------------------	--

## 9 STATISTICAL EVALUATION

### 9.1 Determination of sample size

A Sample size of 16 completers are required for this study. A total of 20 participants will be enrolled in the study accounting for a 20% attrition rate. A formal sample size calculation was not conducted for this study as it is an open-label study.

### 9.2 Analysis Plan

1. The **Safety Population** will consist of all participants who received any amount of product, and whom any safety information is available.
2. The **Intent-to-Treat (ITT) Population** consists of all participants who received product and whom any efficacy information is available.
3. The **Per Protocol (PP) Population** consists of all participants who consumed at least 80% of treatment doses, do not have any major protocol violations, and complete all study visits and procedures connected with measurement of the primary variable.

### 9.3 Statistical Analysis Plan

An efficacy analysis based on the intent-to-treat population will be performed and an efficacy analysis based on the per-protocol population will be performed. Variables will be tested for normality and log-normality. Log-normally distributed variables will be analyzed in the logarithmic domain. Non-normal variables will be analyzed by appropriate non-parametric tests.

Appropriate missing values will be imputed with the most recent previously-available value (LOCF, or “last-observation-carried-forward” imputation). No imputation will be performed for missing values of safety variables.

Data will be summarized in tabular form by visit. Numerical variables will be summarized as mean, standard deviation, standard error of the mean, median, and range (minimum and maximum). Changes from baseline to each subsequent visit will be summarized in the same way, along with a p value indicating whether the mean change is significantly different from zero (based on the paired Student *t*-test, or the non-parametric Wilcoxon Signed-Ranks test). Sensitivity analysis may be conducted as judged by statisticians.

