#### **Secondary outcomes:**

1. Change from baseline to Day 128 in Red Blood Cell (RBC) count, RBC indices (MCV, MCH, MCHC), hematocrit, and Red Cell Distribution Width (RDW) after supplementation with Salmon Protein Hydrolysate Powder (ProGo®)
2. Change from baseline to Day 128 in Hemoglobin (Hb) after supplementation with Salmon Protein Hydrolysate Powder (ProGo®)
3. Change from baseline to Day 128 in relative expression of 84 stress genes (Section 14.5) as evaluated by oxidative stress-related gene RT Profiler PCR array after supplementation with Salmon Protein Hydrolysate Powder (ProGo®)
4. Change from baseline to Day 128 in total Reactive Oxygen Species/Reactive Nitrogen Species free radical activity assessed by ROS/RNS assay after supplementation with Salmon Protein Hydrolysate Powder (ProGo®)
5. Change from baseline to Day 128 in levels of human inflammatory cytokines (IL-1RA, IL-4, IL-6, IL-10, IL-11, IL-13 and TGF- $\beta$ ) as measured by the Multi-Analyte ELISArray after supplementation with Salmon Protein Hydrolysate Powder (ProGo®)
6. Change from baseline to Day 128 in glycated hemoglobin (HbA1c) and fasting glucose after supplementation with Salmon Protein Hydrolysate Powder (ProGo®)
7. Change in score of the Hair, Nails, and Skin Self-Assessment Questionnaire after 128-day supplementation with Salmon Protein Hydrolysate Powder (ProGo®)

[figure not shown]

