#### 4 STUDY DESIGN

This will be an open label study conducted at the KGK clinic in London, ON.

The planned sample size for this study is 20 participants (includes 20% attrition).

Study Arm	Number of Participants
Salmon Protein Hydrolysate (ProGo®)	N = 20

In order to evaluate primary, secondary, and safety outcomes, study assessments will be conducted at baseline and at Day 128.

Protocol 18PEHH:	A proof-of-concept study to evaluate the efficacy of Salmon Protein Hydrolysate Powder on energy increase and anti-inflammatory modulation in healthy males and females.
------------------	--

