## 7.5.8 Future Analyses

### 7.5.8.1 *Oxidative Stress-Related Gene Expression*

Previous *in vitro* experiments using PCR gene-array to evaluate the efficacy of SPH on oxidative stress, showed up- and down-regulation of multiple human oxidative stress-related genes. The present study will evaluate the same effects of the investigational product *in vivo* (Section 14.5).

The PCR array is a highly sensitive and reliable method for the analysis of multiple genes. It will be used to analyze expression levels of 84 genes related to oxidative stress by determining which, if any, oxidative stress genes will be impacted by supplementation with the investigational product.

RNA samples will be prepared for this analysis (Section 7.5.7) and stored at -80 C.

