### 7.5.8.3 *Human Inflammatory Cytokine Levels*

In a previous study, supplementation with the investigational product showed significantly lower IL-6 levels in comparison to a control (Framroze et al., 2016). The current study will evaluate the efficacy of the investigational product on levels of inflammatory cytokines, which includes IL-1RA, IL-4, IL-6, IL-10, IL-11, IL-13 and TGF-β.

Inflammatory cytokine levels will be measured using a multi-analyte ELISArray kit. This kit enables the analysis of protein expression for multiple protein targets.

Serum samples will be centrifuged for 15 minutes at 1000 x g within 30 minutes of collection and then stored at  $\leq -20^{\circ}\text{C}$ .

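### The plan sets out to identify which of 84 genes the product affects but gives only a separate p value per variable; at an assumed two-sided 0.05, an inactive product gives 4.2 nominally significant genes on average.

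*Combined protocol and SAP*

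**What the plan says.** Section 3 lists, as secondary outcome 3, the change from baseline to Day 128 in "relative expression of 84 stress genes". Section 7.5.8.1 gives the purpose of the array as "determining which, if any, oxidative stress genes will be impacted by supplementation with the investigational product". That is a gene-by-gene selection task.

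Secondary outcome 5 covers seven cytokines, and Section 7.5.8.3 states: "The current study will evaluate the efficacy of the investigational product on levels of inflammatory cytokines".

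Section 9.3 is the only analysis rule for either assay. It summarises each change from baseline "along with a p value indicating whether the mean change is significantly different from zero", using a paired t test or, for non-normal variables, a Wilcoxon signed-rank test. This is done in both the ITT and the per-protocol sets.

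No section states a significance level, a multiplicity or false-discovery rule, a fold-change threshold, an ordering of genes, or an exploratory label for these results. Section 9.3 leaves sensitivity analyses to the statisticians' discretion, which does not supply such a rule.

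**The concern.** Section 7.5.8.1 asks a question about 84 genes together; Section 9.3 answers it one variable at a time. If the nominal p values are used to name the affected genes, some will be named by chance. An inactive product can then appear to affect several oxidative-stress genes, and a partly active one yields a list in which true and false genes cannot be told apart. The cytokines carry the same risk on a smaller scale, and they bear directly on the anti-inflammatory half of the study objective. What is at stake is the reliability of the gene and cytokine findings.

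**Working it through.** **Inputs from the documents.**
- Genes: 84 (secondary outcome 3). Appendix V agrees: rows A to G of 12 positions give 7 x 12 = 84 targets, and row H holds reference genes and controls.
- Cytokines: 7 (secondary outcome 5).
- Sample size, Section 9.1: "A Sample size of 16 completers are required for this study". The plan's own enrolment figure reproduces: 16 / (1 - 0.20) = 20.

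**Assumptions, because the plan gives no values.** Two-sided alpha 0.05 per test; equal correlation between the changes of any two genes, varied from 0 to 0.8; effects in units of the SD of within-participant change.

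**1. Expected count if no gene's mean changes.** The expected count is genes x alpha = 84 x 0.05 = 4.2. Expectations add whether or not the tests are correlated, so this needs no independence. At alpha 0.01 it is 0.84; at 0.10 it is 8.4. If every gene went to the exact Wilcoxon test with 16 pairs, the attainable size is 0.0443, giving 84 x 0.0443 = 3.7.

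**2. Chance of at least one.** With independent genes, 1 - 0.95^84 = 0.987. Simulation of 16 pairs with paired t tests gives:

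| Correlation | At least one nominal gene | Median count |
|---|---|---|
| 0 | 99% | 4 |
| 0.3 | 92% | 3 |
| 0.5 | 76% | 2 |
| 0.6 | 64% | 1 |
| 0.7 | about 50% | not recorded |
| 0.8 | 37% | 0 |

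The mean stays at 4.2 while this chance falls, because correlated false positives arrive in clusters: the 95th percentile of the count rises from 8 at correlation 0 to 20 at 0.6. With Benjamini-Hochberg at 0.05, the chance of any call under the null is 5.0%, 4.5%, 4.4% and 3.4% at correlation 0, 0.3, 0.5 and 0.6.

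**3. Cytokines.** Expected count 7 x 0.05 = 0.35. Chance of any: 1 - 0.95^7 = 30% if independent, 21% at correlation 0.6.

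**4. Partly active product.** Suppose 10 of 84 genes truly change.
- False calls expected: 74 x 0.05 = 3.7.
- True calls expected: 10 x 0.85 = 8.5 at 0.8 SD, or 10 x 0.96 = 9.6 at 1.0 SD.
- Ratio of expectations: 3.7 / 12.2 = 30% and 3.7 / 13.3 = 28%.

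The average false share over simulated trials, at correlation 0, 0.3 and 0.5, is:

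| True change | Nominal 0.05 | Benjamini-Hochberg |
|---|---|---|
| 0.8 SD | 29%, 27%, 22% | 4.6%, 4.3%, 3.8% |
| 1.0 SD | 26%, 24%, 20% | 4.3%, 4.2%, 3.6% |

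**5. Can the rule be met with 16 pairs?** The strictest Benjamini-Hochberg step is 0.05 / 84 = 0.0006. The smallest two-sided signed-rank p value is 2 / 2^16 = 0.00003, so the rule is attainable with either test.

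**The case against.** The strongest reply is about context. The title and introduction call this a proof-of-concept study. It is open label, has one primary outcome and no formal sample size calculation, and Section 9.3 attaches the p value to a descriptive table. A reader might infer that the plan declares a gene affected whenever p < 0.05. It does not say so; it is silent on any decision rule. This stands, and it is why an exploratory label is an acceptable minimum. It does not close the gap, because Section 7.5.8.1 still undertakes to identify affected genes and nothing but the per-variable p value is provided for doing so.

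A second reply is that the assays sit under Future Analyses and the blood is shipped to the sponsor, so a separate plan may exist. That is possible. But both assays are listed secondary outcomes, Section 9.3 does not exclude them, and the documents mention no other plan.

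Four stronger readings are not supported:
- **That an inactive product would usually yield some affected genes.** This depends on the correlation. At 0.7 the chance is about even and at 0.8 it is 37%. Only the mean of 4.2 is free of that assumption.
- **That the count doubles because both ITT and per-protocol sets are tested.** The two sets overlap heavily, so 4.2 should be read as the figure for one set.
- **That carrying baseline forward makes the problem worse.** Section 9.3 says "Appropriate missing values will be imputed with the most recent previously-available value" without saying whether these assays are covered. Zero changes would lower power for the t test, but the standard Wilcoxon test discards them.
- **That all other secondary p values need relabelling.** Nothing here bears on hemoglobin, red cell indices, HbA1c, glucose or the hair, nails and skin score.

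**Conclusion.** The concern holds for the 84 genes and the 7 cytokines: the plan poses a selection question and supplies no rule that controls error across the candidates. At an assumed two-sided 0.05, 4.2 nominal genes are expected from an inactive product (about 3.7 with exact Wilcoxon throughout and 16 pairs). The chance of at least one runs from about 99% to 37% over correlations 0 to 0.8, and the documents give no value for that correlation. With 10 genes truly changing by 0.8 to 1.0 SD and correlation 0 to 0.5, about 20-29% of nominal calls are false, against about 4-5% with Benjamini-Hochberg. These false shares rest on the assumed number and size of true changes. The sponsor should make the change; the primary outcome is not affected.

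**What to change.** In Section 9.3, report Benjamini-Hochberg q values beside the p values, across the 84 genes and separately across the 7 cytokines. Call a gene or cytokine changed only if q < 0.05. Treat the unadjusted p values for these assays as exploratory, and refer to this rule in Section 7.5.8.1.

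The minimum alternative, in keeping with a proof-of-concept study, is to label all gene and cytokine p values exploratory and name no affected genes.

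The text and programming cost is small: one paragraph and one line of code. The real cost is power to name genes. With 16 pairs and 10 changed genes, power per gene falls from about 85% to 40% at 0.8 SD, and from 96% to 70-74% at 1.0 SD. If only one gene changes, the strictest step (0.05 / 84) leaves about 20% and 42%. For cytokines, the strictest step (0.05 / 7) leaves 55% and 79%. The unadjusted p values stay in the tables for screening. Neither option separates a product effect from time or assay-batch drift in a single-arm study.

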#### 9.3.1 Premature Discontinuation Description

For each premature discontinuation, the following parameters will be listed: participant number, dates of start and end of treatment, and the reason of premature discontinuation.

#### 9.3.2 Safety

For adverse events, a descriptive analysis will be given. Adverse events will be presented in a frequency table by category and treatment. Furthermore, description, frequency, severity and causality will be reported for each adverse event.

Protocol 18PEHH: A proof-of-concept study to evaluate the efficacy of Salmon Protein Hydrolysate Powder on energy increase and anti-inflammatory modulation in healthy males and females.

Continuous safety parameters (e.g. weight, heart rate and blood pressure) will be summarized using a table including mean, standard deviation, median, minimum value, and maximum value for each measurement point. The changes from baseline will also be summarized similarly.

#### **9.4 Protocol Deviation Description**

Protocol deviations will be listed in the final study report.

#### **9.5 Protocol Amendments**

Once the protocol has been approved by the IRB and Health Canada, any changes to the protocol must be documented in the form of an amendment. All amendments will be documented in the final study report.

### **10 DATA COLLECTION AND STORAGE**

All data collection and record storage will be done in compliance with ICH GCP Guidelines and applicable local regulatory guidelines.

Protocol 18PEHH:	A proof-of-concept study to evaluate the efficacy of Salmon Protein Hydrolysate Powder on energy increase and anti-inflammatory modulation in healthy males and females.
------------------	--

## **11 ETHICAL ASPECTS OF THE STUDY**

This study will be conducted with the highest respect for the individual participants (i.e., participants) according to the protocol, the ethical principles that have their origin in the Declaration of Helsinki, and the ICH Harmonised Tripartite Guideline for GCP.

### **11.1 IRB Approval**

KGK Science Inc. will supply relevant documents for submission to an IRB for the protocol's review and approval. The following must be submitted to the IRB: This protocol, a copy of the informed consent form, and, if applicable, volunteer recruitment materials and/or advertisements and other documents required by all applicable laws and regulations. The IRB's written approval of the protocol and volunteer informed consent must be obtained before commencement of the study. The IRB approval must refer to the study by exact protocol title, number, and version date; identify versions of other documents (e.g., informed consent form) reviewed; and state the approval date.

KGK must adhere to all requirements stipulated by the IRB. This may include notification to the IRB regarding protocol amendments, updates to the informed consent form, recruitment materials intended for viewing by volunteers, local safety reporting requirements and submission of the investigator's annual/final status report to the IRB.

### **11.2 Volunteer Information and Informed Consent**

Written consent documents will embody the elements of informed consent as described in the declaration of Helsinki and the ICH Guidelines for GCP and will be in accordance with all applicable laws and regulations. The informed consent form describes the planned and permitted uses, transfers, and disclosures of the volunteer's personal and personal health information for purposes of conducting the study. The informed consent form further explains the nature of the study, its objectives, and potential risks and benefits, as well as the date informed consent is obtained. The informed consent form will detail the requirements of the volunteer and the fact that he or she is free to withdraw at any time without giving a reason and without prejudice to his or her further medical care.

### **11.3 Potential Risks and Procedures to Minimize Risk**

All potential risks are disclosed to study participants prior to their participation. The potential risks associated with this study include venipuncture. Risks associated with venipuncture include pain, bruising, and infection at the site. Alcohol swabs and proper venipuncture procedure will be followed to minimize the risk of infection.

Protocol 18PEHH:	A proof-of-concept study to evaluate the efficacy of Salmon Protein Hydrolysate Powder on energy increase and anti-inflammatory modulation in healthy males and females.
------------------	--

## **12 QUALITY ASSURANCE AND QUALITY CONTROL**

### **12.1 Auditing**

All material used in clinical studies are subjected to quality control. Quality assurance audits may be performed by the sponsor or any health authority during the course of the study or after its completion. The Investigator agrees to comply with the sponsor and regulatory requirements in terms of auditing of the study. This includes access to the source documents for source data verification.

### **12.2 Monitoring**

An initiation meeting will be conducted by the sponsor or an approved representative (CRO). At this meeting, the protocol and logistical aspects of the study will be reviewed with the Investigator and all study staff.

Source documents will be reviewed to ensure that all items have been completed and that the data provided are accurate and obtained in the manner specified in the protocol. The participant files will be reviewed to confirm that:

1. Informed consent was obtained and documented
2. Enrolled participants fulfilled all inclusion criteria and did not meet any exclusion criteria;
3. AE/SAE reporting has been performed as applicable
4. Study visits have been conducted as per protocol and information has been recorded in the appropriate place in the source document
5. The study product is being stored correctly and an accurate record of its dispensation to the study participants is being maintained (accountability)

Incorrect, inappropriate, or illegible entries in the participant files will be returned to the Investigator or designee for correction. No data disclosing the identity of participants will leave the study center. The Investigator and any designees will maintain confidentiality of all participant records.

The Investigator will permit trial-related monitoring, audits, IRB/IEC review, and regulatory inspections and will allow direct access to source data and documents for these purposes.

